4.7 COMPENSATION

Participants will be compensated for their time and travel with 2000 rubles (approx. USD 30) in currency each for their baseline assessment and for their participation at 1- and 6-month follow-up visits. Participants who complete an ACT session without an assessment will receive the same amount. Participants who complete phone assessments for the follow-up visits will be compensated 500 rubles for their participation with cash or a phone card (this will be offered as a last resort option for the 1-month and 6-month assessments). All participants who conduct their follow-up assessments over the phone due to COVID-19, will still receive full compensation (2000 RUB). Participants who arrive 1 hour late or more to a session will receive partial

compensation (1000 rubles). Participants who arrive with only 30 minutes remaining in the session will receive no compensation.

Similar compensation has been used in a previous collaborative Russian-Boston research study and was deemed by the PSMU IRB to be an appropriate, non-coercive amount of funds for involvement in a clinical research project.

4.8 RETENTION

Baseline visit: Retention begins at baseline by ensuring that the participant enjoys the experience of participating in the study, by explaining the informed consent and what would happen in the study, and by carefully collecting contact information, including both the address where the participant is registered and the address where the participant is currently staying. Participants will be asked to provide contact information for up to 4-5 alternative contacts (although only 2 will be required as per eligibility criteria), who may know their whereabouts. Alternative contacts can include friends, family members, and social workers. Participants will be asked if any of their friends are participating in the study and to include them as alternative contacts, if possible. Contact numbers must be verified by calling the numbers with the participant present, using the following script: “I work with a team at the Center of Medical Rehabilitation #1. Your friend/relative [NAME] is here with me and just enrolled in a study. He/she has listed you as an alternative contact. We will only call you if we are having trouble reaching [NAME] to see if you can help us connect with them. Today I am just calling to confirm that this number is active.”

Participants will also be asked for their email address and membership to any social networking platforms.

All visits: Participants will be offered tea, coffee, water, and snacks at each study visit to make their experience in the research study more enjoyable.

RA will offer to help participants add the next scheduled study visit to the calendar in their phone and set a reminder in their phone.

Follow up visits: Contact information for participant and alternatives will be reviewed and updated at every visit.

Other strategies: Participants will be contacted by telephone with appointment reminders and email if one is provided. The study team will also utilize social networking to connect with participants. If participants are unable to be reached via phone, in addition to attempting to reach them via text messaging and email, participants will be sent private messages on Vkontakte (Russian social network) utilizing an existing standard script to remind them of their upcoming study visit. No sensitive information will be revealed or ascertained using this method.

Standard reminder text: This is a reminder that your visit to the Center of the Medical Rehabilitation #1 is scheduled for _____ at _____. Please reply to confirm or call [name] to reschedule.

Study participants will be asked to contact the study team if their phone number changes between study visits; participants will be compensated 200 rubles (USD 3) in currency for this information. All no-shows will be followed up to reschedule appointments.

Participants will receive a card with clear instructions on how to arrive to the study site.

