6. PARTICIPANT SAFETY

Boston Medical Center, First St. Petersburg Pavlov State Medical University/Global Health Institute and their Institutional Review Boards (IRB), the Principal Investigator ([name]) and the site PI and project manager are responsible for monitoring the pilot RCT proposed for the R00 phase and for ensuring the safety of participants. As the research is conducted in Russia, [name] will verify at each weekly conference call meeting if any adverse events or unanticipated problems occurred. The Russian investigators will notify the PI by email of serious incidents the same day. Discussion will take place on whether or not the incident meets the definition of an Unanticipated Problem (UP): is unexpected, possibly related to being in the research, and places subjects or others at greater risk of harm. Discussion will also take include if protocols or consents need to be modified, and if/when the incident should be reported to the IRBs. The principal risk of the study is breach of confidentiality. The remaining risks are minimal.

Participation in this study presents “minimal risk” which is defined as “the probability and magnitude of harm or discomfort anticipated in the research are not greater in and of themselves from those ordinarily encountered in daily life or during the performance of routine physical or psychological examinations or tests,” (from 45 CFR 46.102(i)). The primary risk of the study is the risk of loss of confidentiality. This risk and

any other risk of study participation are addressed above and within Protection of Human Subjects. The risk of breach of confidentiality is best addressed by appropriate study procedures; however, the PI will be responsible for assuring that study procedures are adhered to regarding data security, data transfer, and communications in tracking participants by meeting regularly with study staff, reviewing procedures, and performing quality control reviews of study forms as described above.

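### The compulsory contact-verification script tells third parties that a named participant has enrolled in a study at a named rehabilitation center, which checking a phone number does not require

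*Combined protocol and SAP*

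**What the plan says.** Section 4.8 (Retention) sets out how tracing contacts are collected at baseline. Up to four or five are sought; two are mandatory, because Section 2.7 makes them an inclusion criterion. On who they may be: "Alternative contacts can include friends, family members, and social workers". On co-participants: "Participants will be asked if any of their friends are participating in the study and to include them as alternative contacts, if possible".

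The check on each number is not optional: "Contact numbers must be verified by calling the numbers with the participant present". The wording is fixed. The caller opens with "I work with a team at the Center of Medical Rehabilitation #1", then says that the named friend or relative "is here with me and just enrolled in a study. He/she has listed you as an alternative contact". The script goes on to say that the contact will be called only if the team cannot reach the participant, and that today's call is just to see that the number is in service.

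Section 6 (Participant Safety) states: "The principal risk of the study is breach of confidentiality". Section 4.3 (Screening), in its steps against double enrolment, has the research assessor carry out the name search so that a newcomer does not learn that a namesake is already enrolled. The stated reason is the enrolled person's confidentiality.

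**The concern.** The script gives away more than its task needs. A relative, friend or social worker learns from study staff that a named person is with someone from a named rehabilitation center and has joined research. Section 1.1 describes the people eligible for this trial as highly stigmatized in the country where it runs, so even indirect information of this kind may matter to them.

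The prompt to list co-participants adds to this. Everyone enrolled meets the same entry criteria, so for someone who knows those criteria, learning that a person has enrolled amounts to learning that person's health and drug-use status.

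What is at stake is participant protection. Sample size, power, type I error and the comparison between arms are not affected: Section 4.5 lists number verification at the baseline visit ahead of randomization, for everyone.

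**Working it through.** No figure in the plan depends on this point, so the check is mainly a comparison of texts, followed by a count of calls.

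**1. What the call is for, against what it says.** The stated purpose is to confirm a working number. Three things are said beyond that: the caller's institution, the participant's presence with the caller, and the enrolment. Confirming the number, and asking whether it may be used to reach the participant, requires a name the contact recognises. It does not require the center or the study.

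**2. How much choice the participant has.** The participant decides whom to name. But fewer than two contacts means ineligibility (Section 2.7), verification is compulsory (Section 4.8), and no alternative wording or method of verification is described. The choice is over who hears the script, not over what it says.

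**3. What a contact can infer.**
- *Ordinary contact:* a link to a rehabilitation center and enrolment in an unspecified study. HIV and drug use are not mentioned.
- *Co-participant:* the same words, heard by someone who knows the center and has been screened for the same study. Inclusion criteria 2, 3 and 4 in Section 2.7 require HIV infection, injection in the past 30 days and no current ART. A co-participant who recognises the study could infer all three.

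Listing a friend as a co-participant means that the participant already knows of the friend's enrolment. It does not mean that the friend knows of the participant's; the call may be how the friend finds out.

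**4. Consistency with other safeguards.** Section 4.3 conceals one person's enrolment from another. Section 3.3.A invites pseudonyms in group sessions. Section 4.8 has staff announce enrolment by name and encourages contacts for whom that is most informative.

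**5. Number of calls.** Inputs: 100 randomized participants (Section 2.4); two contacts required (Section 2.7); up to four or five sought (Section 4.8).
- Minimum: 100 × 2 = 200 calls.
- If all contacts sought are given and verified: 100 × 4 = 400 to 100 × 5 = 500 calls.

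This assumes one call per contact at baseline. It does not estimate harmful disclosures: some calls will go unanswered, some contacts may already know, and one person may be listed by several participants.

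**The case against.** The strongest reply is that contact chosen by the participant is not a breach. The participant supplies the names, has given written consent by then (Sections 4.4 and 4.5) and is in the room during the call. The script is silent on HIV and drug use. Section 6 says the risk is also dealt with in a human-subjects text that is not part of these documents, and the consent pages are not available, so it cannot be said that participants did not agree to this wording. All of this stands, and it limits the point to an avoidable exposure. Consent would not, however, make the extra information necessary to the call.

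The contrast with Section 4.3 can also be called loose, since that section protects someone from a stranger they did not choose. That is fair as far as it goes. In the intervention arm, group sessions of about five make co-participation visible anyway; but the 35 planned controls attend no groups, and a group shows its members only to each other.

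A reader might infer four further things that the documents do not support:
- *That the appointment reminder is a second disclosure to third parties.* It begins "This is a reminder that your visit to the Center of the Medical Rehabilitation #1 is scheduled for", is addressed to the participant and mentions no study. The assurance "No sensitive information will be revealed or ascertained using this method" concerns private social-network messages, not the verification call, so the call does not contradict it.
- *That naming enrolled friends reveals their status to staff.* The research assessors screened and assessed those friends and already know it.
- *That adverse-event counts will be too low.* Section 6.1 does not say whether a scripted call counts as a breach, so this is conjecture.
- *That the calls raise the stigma scores.* Nothing in the documents shows this.

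**Conclusion.** The point holds as a modest matter of participant protection. A compulsory, fixed script discloses study enrolment and a named rehabilitation center when its stated task needs neither, in a trial whose own leading risk is loss of confidentiality. The exposure is indirect for most contacts and most informative for contacts who are themselves participants.

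The size is 200 calls at the minimum and 400 to 500 at the ceiling, counted as calls only. It would be tempting to read the procedure as a breach in itself, or the call count as a count of harms. Neither follows, given the participant's presence and choice of contacts and the unavailable consent text.

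The conclusion assumes that the script is used as written, and that a co-participant can recognise the study from the center's name and the mention of enrolment.

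**What to change.** Replace the script in Section 4.8 with a neutral one: confirm that the number is active and may be used if the participant cannot be reached, without mentioning a study, enrolment or the center.

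Reconcile the request to list co-participants with the safeguard in Section 4.3, for example by no longer prompting for them.

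The cost is a wording change, submitted to both IRBs before use as the protocol requires for any amendment. It needs no extra staff or visits, and the two-contact criterion is untouched. The drawbacks are that some contacts may be warier of a caller who gives less away, and that a few tracing contacts may be lost. The documents give no figures from which to estimate either.

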5. ASSESSMENTS

5.1 BASELINE ASSESSMENT

The baseline assessment will be conducted immediately following the screening and informed consent. The assessment will be interviewer-administered.

Participants will be assessed as part of this study using validated interview instruments covering the following topics, which will take approximately 60 min:

- Demographics, modified from the ASI Lite-CF Clinical/Training Version and Addiction Severity Index⁷
- ART Medication Use and Adherence
- HIV Sex Risk Behaviors, questions are adapted from the Women's Health Coop Baseline Questionnaire
- HIV Risk Categories, using questions adapted from the American Red Cross and Navaline et al.¹⁷
- HIV Disclosure, using questions from Stein et al. (1998)¹⁸ and Raj et al. (2006)¹⁹
- HIV Stigma, using the Berger et al. HIV stigma scale²⁰ and Leickness et al.
- Substance Use Stigma^{21, 22}, via a modified Substance Abuse Self-Stigma Scale
- Substance Use enacted interpersonal stigma, through the Stigma-Related Rejection Scale (SRS)
- Psychological flexibility, by the Acceptance and Action Questionnaire – Substance Abuse (AAQ-SA)
- Mental health through the Patient Health Questionnaire (PHQ-9)
- Anxiety by the GAD-7
- Partner Violence and Sexual Assault, adapted from the TAJ assessment
- Alcohol Use, via the AUDIT-C²⁸
- Perceived alcohol stigma, using questions from Luoma et al. (2010)
- Drug use by an adapted version of the Risk Behavior Survey^{30, 31}
- Overdose and Suicide, using adapted questions from Britton et al. (2012)³⁴
- Social Support, using the harmonized STTR document^{35, 36}
- VR-12 Health Survey & MOS-HIV^{37, 38}
- Care utilization
- Post-Traumatic Stress Disorder via the Abbreviated PTSD Checklist
- Police involvement
- HIV Testing History

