2.6 STUDY SITES

Participants will be recruited through a civil society organization (CSO) providing street outreach services to PWID and people living with HIV in St. Petersburg, Russia. CSOs serving PWID and PLWH have been historically funded by the Global Fund; currently, they are financed mostly by foundations and private donations. All are closely monitored by the Russian authorities. They have no specific rules on medical privacy, other than providing an inviting, safe haven for affected people, who congregate at the CSOs for support and mutual help. The latter offer counseling, but usually have no medical staff and do not offer therapy.

All assessments and group trainings will be conducted at a rehabilitation center. Street outreach CSOs do not have facilities to conduct study procedures, but have connections with other organizations, such as rehabilitation centers, and thus participants recruited from the CSOs will be transported to these organizations for all other study procedures. The rehabilitation centers have the resources and capacity to conduct the assessments and intervention. Therefore, this collaboration with the CSOs is a multi-institutional approach to reach individuals in a highly stigmatized population and help them address the negativity in their lives related to other people's attitudes about their HIV status and substance use.

Recruitment will be completed by the CSO staff and phone-screening will be completed by the rehabilitation center staff, who are trained as research assessors (RAs) by academic staff at PMSU. In-person screening, informed consent, and assessments will also be completed by RAs. Intervention sessions will be completed by trained ACT interventionists on site at the rehabilitation center or at the Laboratory of Clinical Pharmacology of Addictions at the First St. Petersburg Pavlov State Medical University (PSMU) in St. Petersburg, Russia. PSMU is the major educational, scientific, and clinical medical institution for northwestern Russia. The ACT interventionists are both rehabilitation center staff and PMSU staff, who were trained in ACT for this study by the PI and master trainer consultants in a workshop modified for the Russian context, conducted from March 2 through March 9, 2019.

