3. INTERVENTION

3.1 INTERVENTION OVERVIEW

The study will randomize 100 PWID living with HIV in the St. Petersburg area. We will approach potential participants at CSOs serving PWID and people living with HIV (PLWH). After a phone-screening, potential participants will be given clear transportation instructions to the location of the remainder of the procedures (in-person screening, consent, enrollment, assessments, intervention sessions). After in-person screening, consent, enrollment, and the baseline assessment, participants will be randomly assigned to either the SCRIPT intervention or standard of care. Following randomization, participants in both groups will receive standard of care at the study site.

Following randomization by RAs at the rehabilitation center, participants in the intervention group will be scheduled to engage in group ACT sessions. These will consist of three 2-hour group sessions of culturally adapted ACT to reduce stigma and related manifestations in weeks 1, 2 and 3. The ACT sessions are described in further detail in 3.3.A.

Throughout the course of the study, participants will be expected to participate in three in-person assessments (baseline, 1 month [4 weeks], and 6 months [24 weeks]). Participants in the intervention groups will receive three ACT sessions over one month in approximately 13 groups of 5 people each (n=65), with a final assessment conducted at 6 months.

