5.2 FOLLOW UP ASSESSMENTS

Phone assessments will be permitted for 6 month assessments, as a last resort, for participants who are unable to come in-person. The 1 month assessment will take about 45 minutes, the final assessment at 6 months will take about 60 min.

Administered Assessment	Baseline	1-Month	6-Month
Demographics	X		
ART Use and Adherence	X	X	X
HIV Sex Risk Behaviors	X	X	X
HIV Risk Categories	X		
HIV Disclosure	X		X
HIV Stigma	X	X	X
Substance Use Stigma	X	X	X
Substance Use Daily Life Experience (SRS)	X		
Acceptance and Action (AAQ-II – SA)	X	X	X
Patient Health Questionnaire (PHQ-9)	X	X	X
Anxiety (GAD-7)	X	X	X
Partner Violence and Sexual Assault	X		
Alcohol Use: AUDIT-C	X		
Perceived Alcohol Stigma	X		
Drug Use	X	X	X
Overdose	X		X
Social Support Scale	X		X
VR-12 Health Survey	X		X
Health Care Utilization	X		X
Abbreviated PTSD Checklist	X		
Involvement with Police	X		X
[‡] Satisfaction with the Intervention		X	
*HIV Testing History	X		
^a COVID-19 testing history, risk behaviors, and perceptions			X

[‡]Intervention group participants only

*If this information is not collected at baseline, RAs will collect this information at a later study visit.

^a Not administered to all 6-month participants

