The Ukrainian Institute on Public Health Policy (UIPHP) will design, develop and maintain the electronic data collection forms, participant and data tracking, and underlying database systems, and implement procedures for data quality control, including multiple checks for entered data. Electronic data collection forms will be designed to read easily, have clear instructions, preprogrammed skip patterns, real-time range checks and internal logic to minimize missing data and result in "cleaner" data at capture. Electronic data collection forms, including randomization module, participant and data tracking, will be developed in REDCap (Research Electronic Data Capture), a web application located at UIPHP server. The REDCap platform has no hard requirements with regard to server processing power, memory or hard drive space since it is not resource-intensive and requires very little initial drive space by either the web server or database server. The application employs various methods to protect against malicious users who may attempt to identify and exploit any security vulnerabilities in the system. The REDCap users have access only to data and information that they are supposed to have within the application by identifying user privileges. Each user has their own account, and their user account will only have access to REDCap projects that they have created themselves or to projects which other users have granted them access. REDCap contains an auto-logout setting, which is customizable (default auto-logout time is 30 minutes), and will automatically log a user out of the system if they have not had any activity (e.g. typing, moving the mouse) on their current web page for the set amount of time. This prevents someone else from accessing their account and their project data if they leave a workstation without properly logging out or closing their browser window. REDCap maintains a built-in audit trail that logs all user activity and all pages viewed by every user, including contextual information (e.g. the project or record being accessed). Therefore, a REDCap project administrator will be able to monitor any activity in the project, e.g. entering data, exporting data, modifying a field, running a report, or add/modifying a user. Study forms will be completed according to the schedule below.

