9. STAFF TRAINING

9.1 TRAINING OF STUDY STAFF

All study staff will be trained on the study protocol. Training will take place in-person in Tbilisi, Georgia, St. Petersburg, Russia, and via webinars.

Recruitment will be performed by a CSO outreach worker who has extensive experience working with this population. In-person screening, enrollment, and all assessments will be performed by Research Assessors (RAs) who have experience working with this population. The staff are trained to assess for adverse events and will follow established protocols for identifying and monitoring any ongoing adverse events.

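### No assessor masking is specified: the research assessor role both randomises and interviews for the subjective primary outcomes, and satisfaction is collected by staff of the centre that supplies some of the interventionists

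*Combined protocol and SAP*

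**What the plan says.** **Who does what.** Section 2.6 states "In-person screening, informed consent, and assessments will also be completed by RAs", and section 9.1 repeats it: "In-person screening, enrollment, and all assessments will be performed by Research Assessors (RAs) who have experience working with this population". Section 3.1 introduces the scheduling of ACT sessions with "Following randomization by RAs at the rehabilitation center", and section 4.5 places randomisation at the baseline visit.

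**How outcomes are collected.** For baseline, section 5.1 says "The assessment will be interviewer-administered". For follow-up, section 4.5 lists administering the questionnaire among the RA's tasks at 1 and 6 months. Section 4.6 lets the RA nudge a participant whose answers conflict towards more consistent ones, without forcing a change.

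**Satisfaction.** This is the Aim 1 primary outcome (section 2.1). The schedule in section 3.5 puts it inside the 1-month assessment, and the footnote in section 5.2 limits it: "Intervention group participants only".

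**Staffing and systems.** The RAs are rehabilitation-centre staff (section 2.6). Of the providers the same section says "The ACT interventionists are both rehabilitation center staff and PMSU staff". Section 7.3 says "The REDCap users have access only to data and information that they are supposed to have within the application by identifying user privileges", and the same system holds the randomisation module and participant tracking.

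**Masking.** No section masks outcome assessors. Blinded data are mentioned only in the general description of the DSMB (section 6.2).

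**The concern.** The Aim 2 primary outcomes are two internalised-stigma scales at 1 month, answered aloud to an interviewer. Section 3.3.A has ACT participants told that the groups are meant to help with stigma and shame, so the favourable answer is easy to guess. An interviewer who knows the arm can, without intending to, phrase, probe or resolve inconsistent answers differently by arm. A differential shift of that kind looks like a treatment effect, and the t-tests in section 8.1 cannot separate the two afterwards.

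Satisfaction has a different problem. Participants rate the sessions face to face with an employee of the centre that also employs some of the people who ran them. The likely result is courtesy bias, which would flatter the feasibility conclusion for Aim 1.

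**Working it through.** The documents give no alpha, power, SD or effect size, so there is no planned figure to reproduce. The check has two parts.

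**1. Can an interviewer know the arm at follow-up?**

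- Allocation: the RA role randomises (sections 3.1 and 4.5) and performs all assessments (section 9.1).
- Timing (section 3.5.A): the 1-month target is 30 days after the first group session for ACT, but 30 days after baseline for control. With the first session at its target of day 7, the ACT visit falls on day 7 + 30 = 37, against day 30 for control. If the first session is on the last day of its window, the ACT target is day 31 + 30 = 61. Whoever schedules the visit sees the arm.
- Content: satisfaction items appear only for ACT participants, within the 1-month assessment (sections 3.5 and 5.2).
- Role overlap: section 6.2 describes RAs and interventionists together, by profession, and nothing bars one person from holding both roles.

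The arm is therefore open to the interviewing role through several routes, and no provision closes any of them.

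**2. What could an arm-dependent shift do to a stigma comparison? (illustration only)**

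- Arm sizes 65 and 35 are from section 2.4. Two-sided alpha 0.05 and the shift sizes b are assumptions. There is no true effect.
- Standard error in SD units: sqrt(1/65 + 1/35) = sqrt(0.01538 + 0.02857) = 0.210.
- False-positive rate = P(|Z + b/SE| > 1.96).

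| Assumed shift b | b/SE | False-positive rate |
|---|---|---|
| 0 | 0 | 5.0% |
| 0.1 SD | 0.48 | 7.6% |
| 0.2 SD | 0.95 | 15.9% |
| 0.3 SD | 1.43 | 29.9% |

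Sensitivity at b = 0.2 SD:

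- Assumed 20% loss in both arms (52 versus 28): SE = sqrt(1/52 + 1/28) = 0.234, rate 13.7%.
- Assumed ICC of 0.05 in ACT groups of 5: design effect 1 + 4 × 0.05 = 1.2, SE = sqrt(1.2/65 + 1/35) = 0.217, rate 15.2%.
- Assumed ICC of 0.10: design effect 1.4, SE = 0.224, rate 14.5%.

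For scale, the difference detectable with 80% power is (1.96 + 0.84) × 0.210 = 0.59 SD without clustering or loss. A shift of 0.2 SD is about one third of that.

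None of this applies to satisfaction. It has no control counterpart, so no between-arm false-positive rate exists for it.

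**The case against.** This is a pilot feasibility trial of an intervention to which participants cannot be blinded. They know their arm and report on themselves, so masking the interviewer removes only part of any bias. That stands, and it limits what the table above can be used for.

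Four stronger readings are tempting and are not supported:

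- *That the individual who randomises a participant also interviews that participant.* The documents assign tasks to a role. Nothing says it is the same person, and nothing prevents it. The sentence in section 5.1 concerns baseline, before any arm exists; follow-up interviewing rests on section 4.5.
- *That all interventionists are the RAs' colleagues.* Only some are; the others are university staff.
- *That masking could be had for nothing.* The number of RAs, their workload and the budget are not stated. Rotating RAs and changing one permission would also not be enough. Section 7.3 describes access by user and project, not by participant, while a rotating RA would need to see the allocation of some participants and not of others. Scheduling and contact updates would still reveal the arm.
- *That masking would protect satisfaction.* Whoever asks those items knows the arm by definition.

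There are also practical objections. Private completion does not fit a telephone visit: section 4.7 allows one as a last resort at both follow-ups, section 5.2 only at 6 months. The past-tense randomisation text (section 3.2) and the COVID-19 provisions (sections 4.7 and 5.2) suggest that enrolment may already be under way. If so, a change of mode would mix interviewed and self-completed satisfaction scores. These points bear on how the fix is made, not on whether the gap exists.

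**Conclusion.** The point holds in this form: no assessor masking is specified, one role randomises and interviews for the primary outcomes with the arm readily apparent, and satisfaction is collected in a setting that invites courtesy bias. That the arm is known to interviewers is a strong inference from the procedures, not a statement in the plan.

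The size of the bias is unknown. A reader might take 15.9% as the trial's error rate, but it is only what an assumed 0.2 SD arm-dependent shift from any source would produce. The interviewer's share of such a shift cannot be estimated from the documents. The courtesy bias in satisfaction is unquantified. The change is worth making because the exposure is avoidable in part and cannot be corrected in analysis.

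**What to change.** 1. **Satisfaction.** Have the participant complete the module privately, on paper or tablet with reading help on request, after the stigma scales and all other items. At a telephone visit, have it asked by someone who is neither an interventionist nor the outcome interviewer. Record the mode for every participant, so that scores can be shown by mode if the change comes after enrolment has begun.
2. **Separation of roles.** Give randomisation, ACT scheduling and arm-revealing tracking forms to an existing role that does not interview, for example the local study coordinator (section 4.6). Pass interviewers an appointment date only. Restrict their REDCap access to allocation and session records. Bar anyone who delivers ACT from outcome interviews.
3. **Six months.** Where staffing allows, use a different RA from the one who handed over the satisfaction module. Log each unmasking, and state in the protocol that unmasked assessment is a limitation.

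The cost is some coordinator workload, less continuity of interviewer, and help for participants with low literacy. It is low subject to staffing, which the documents do not describe. Residual bias remains because participants know their arm. If the roles cannot be separated, the order of the modules and private completion of satisfaction can still be adopted alone.
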